7.1.2.1 Subjects Prematurely Transitioned to the Baxalta Continuation Study

Bleed data for the period from transitioning to the Baxalta Continuation study up to the nominal ObsDay 364 will be obtained in the form of a RAW data export from the Baxalta Continuation study. This transfer will be filtered to contain only the applicable subject numbers identified as having transitioned too early.

The following fields/variable will be utilized for these subjects from the Baxalta Continuation study:

- Unique subject number (for matching across studies).
- Bleed cause (Spontaneous, unknown, injury related).
- Bleed type (Joint, non-joint).
- Onset date of bleed.
- End date of bleed/Ongoing.

- Anatomical bleeding site.
- Severity of bleed.
- Treatment administered for bleed (BAX 855, other: specify, none).
- If treated with BAX 855:
- Efficacy rating.
- Infusion date/time.
- Amount infused (IU/kg).

This data will be incorporated into to the SDTM database with flag or category added that would enable the identification of this data as having its source post-PROPEL. For the statistical analyses (primary, secondary and exploratory), this data will be treated as would have been if recorded during PROPEL itself (i.e. observed data).

7.1.2.2 Subjects Prematurely Leaving PROPEL Without Transition to Other Baxalta Study

These subjects will be approached requesting their willingness to provide information regards their bleeding status for the time from leaving PROPEL up to at least nominal ObsDay 364. Should the subject consent, the subject information will be incorporated into the PROPEL RAW data base in one of the following ways:

- If the subject confirms no bleeding episodes occurred during the enquired period, it will be entered as such on the Completion/Termination eCRF page.
- If the subject reports bleeding episodes, the following will be requested from the subject for entering on the Bleeding Episode eCRF pages:
 - Bleed cause (Spontaneous, unknown, injury related).
 - Bleed type (Joint, non-joint).
 - Onset date of bleed.
 - End date of bleed/Ongoing.
 - Anatomical bleeding site.
 - Severity of bleed.

No further bleed related information such as treatment provided for the bleeds will be collected as it beyond the scope of the PROPEL protocol. The data collected for these subjects will be flagged to enable the identification of it as being collected post-PROPEL. For the statistical analyses (primary, secondary and exploratory), this data will be treated as if captured during the PROPEL study (i.e. observed data).

7.2 Analysis of Secondary Efficacy Outcome Measures

The following secondary efficacy outcome measures are discussed in Section 7.1.2:
Bleeding Episodes:

- Total, Spontaneous, and Injury Related (Traumatic) ABR, and Spontaneous AJBR.
- Overall hemostatic efficacy rating at 8 hours (± 1 hour) after initiation of BAX 855 infusion for the treatment of the bleed as well as at the resolution of the bleed.
- Number of BAX 855 infusions needed for the treatment of bleeding episodes.
- Intra-, post- and perioperative hemostatic efficacy in case of surgery.
- Intra- and postoperative blood loss in case of surgery.

The following are the other secondary efficacy measures that are discussed in this section:

- HJHS questionnaire.
- Haemo-SYM questionnaire.
- Physical domain and component scores of the SF-36 questionnaire.
- EQ-5D questionnaire.
- Healthcare resource utilization (as recorded in the subject diaries).
- Subject physical activity levels.
- The total weight-adjusted consumption of BAX 855 for each treatment arm.

Subject listings will be presented for the following items using the SAS:

- HJHS questionnaire.
- Haemo-SYM questionnaire
- SF-36 questionnaire.
- EQ-5D questionnaire.
- Health resource usage and events.
- Physical activity.

Summary tables containing descriptive statistics and comparisons, using the Wilcoxon signed rank and Mann-Whitney U tests, will be presented on the following items using the FAS:

- The HJHS questionnaire.
- The Haemo-SYM questionnaire.
- The SF-36 questionnaire.
- The EQ-5D questionnaire.
- Health Resource Use.

A summary table containing descriptive statistics only of subject physical activity will also be presented. The summary tables should be presented by age group.

The following information item is obtained from the eCRF:

- Haemophilia joint health score (*Joint score [HJHS] eCRF panel*).

The following information items are obtained from the ERT third party vendor diary data:

- Haemo-SYM item responses and scores.
- SF-36 item responses and scores.
- EQ-5D item responses and scores.
- Health resource utilization.
- Physical activity records.

7.2.1 Haemophilia Joint Health Score (HJHS) Questionnaire

The HJHS is a questionnaire based assessment of the physical structure and function of the joints in subjects with haemophilia. Each joint is assessed in terms of swelling, muscle atrophy, crepitus on motion, extension, flexion loss, joint pain and joint strength. A global gait score is separately assessed, ranging from '0' (indicating all skills are within normal limits), to '4' (indicating that no skills are within normal limits). The global gait score combined with the joint scores, forms the HJHS total score. A lower HJHS score indicates a better condition of the joint. Therefore, negative change scores indicate that symptoms have improved.

The questions in the HJHS questionnaire are scored as set out in Table 1:

Table 1 HJHS Questionnaire Item Scores

Item	Score
Swelling	No Swelling: 0
	Mild: 1

Item	Score
	Moderate: 2
	Severe: 3
	Non evaluable: No score
Duration (Swelling)	No Swelling or < 6 months: 0
	≥ 6 months: 1
	Non evaluable: No score
Muscle Atrophy	None: 0
	Mild: 1
	Severe: 2
	Non evaluable: No score
Crepitus on Motion	None: 0
	Mild: 1
	Severe: 2
	Non evaluable: No score
Flexion Loss	< 5 degrees: 0
	5 degrees to 10 degrees: 1
	11 degrees to 20 degrees: 2
	> 20 degrees: 3
	Non evaluable: No score
Extension Loss	< 5 degrees: 0
	5 degrees to 10 degrees: 1
	11 degrees to 20 degrees: 2
	> 20 degrees: 3
	Non evaluable: No score
Joint Pain	No pain through active range of motion: 0
	No pain through active range; only pain on gentle overpressure or palpitation: 1
	Pain through active range: 2
	Non evaluable: No score
Strength	Holds test position against gravity with maximum resistance (gr.5): 0
	Holds test position against gravity with moderate resistance (but breaks with maximum resistance (gr.4): 1
	Holds test position with minimal resistance (gr.3+) or holds test position against gravity (gr.3): 2
	Able to partially complete ROM against gravity (gr.3-/2+), or able to move through ROM gravity eliminated (gr.2-): 3
	Trace (gr.1) or no muscle contraction (gr.0): 4
	Non evaluable: No score
Global Gait Score	All skills are within normal limits: 0
	One skill is not within normal limits: 1
	Two skills are not within normal limits: 2
	Three skills are not within normal limits: 3
	No skills are within normal limits: 4
	Non evaluable: No score

The following derivations will be made based of the eCRF reported results:

- The joint totals (per assessment) are calculated as:

$$\text{Joint Totals} = \sum \text{Individual item scores per joint within a subject}$$

- The sum of joint totals (per assessment) is calculated as:

$$\text{Sum of Joint Totals} = \sum \text{Joint totals within a subject}$$

- The HJHS total score is calculated as:

$$\text{HJHS Total Score} = \text{Sum of Joint Totals} + \text{Global Gait Score}$$

A Wilcoxon Signed Rank test for paired samples will be used to assess the within treatment arm change in HJHS total score between baseline and completion for any significant statistical differences. The following SAS[®] code can be used:

```
Proc Univariate Data = <Dataset>;  
  Var <Change>;  
  By <Treatment>  
  ODS Output TestsForLocation = <Outdata>  
  (WHERE = (test = 'Signed Rank'));  
Run;  
Quit;
```

Where <Dataset> refers to the input dataset, <Change> the change from baseline at the completion visit, <Treatment> then assigned treatment arm and <Outdata> the resulting dataset from the procedure containing the inferential statistics for presentation.

A Mann-Whitney U test will be used to assess the between treatment arm change in HJHS total score from baseline to completion for any significant statistical differences. The exact p-value should be selected and presented. The following SAS[®] code can be used:

```
Proc NPAR1WAY Data = <Dataset> Wilcoxon;  
  Class <Treatment>;  
  Var <Change>;  
  exact Wilcoxon /MC;
```

```
ODS Output Wilcoxonetest = <Outdata>;  
Run;  
Quit;
```

Where <Dataset> refers to the input dataset, <Treatment> the assigned treatment arm, <Change> the change from baseline at the completion visit and <Outdataset> the resulting dataset from the procedure containing the inferential statistics for presentation.

Statistical significant differences are present if a p-value of <0.05 is obtained.

Values for the Wilcoxon Rank Sum and Mann-Whitney U tests will be selected using the distribution based, $\frac{1}{2}$ standard deviation minimal important difference (MID) threshold as promoted by Norman et al³. Change in subject HJHS total score from baseline at the completion visit $> \frac{1}{2}$ SD of the baseline total scores across all subjects should be considered a MID and will be included in both the Wilcoxon Rank sum test as well as the Mann-Whitney U test.

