22. PERIOPERATIVE MANAGEMENT

22.1 Types of Interventions

22.1.1 Major Surgeries

Major surgeries involve surgeries which require moderate or deep sedation, general anesthesia, or major conduction blockade for patient comfort. It generally refers to major orthopedic (e.g., joint replacement), major abdominal, intracranial, cardiovascular, spinal and any other surgery which has a significant risk of large volume blood loss or blood loss into a confined anatomical space. Extractions of several teeth or extraction of the third molar are generally considered as major. In children it may include adeno-tonsillectomy. Examples include:

- bone fixation for fractures
- hip and knee replacements (arthroplasties)
- arthrodeses (joint fusions)
- open synovectomies
- osteotomies
- liver biopsy
- pseudotumor removal, hepatectomy, colectomy, tumor removal,
- hardware removal (plates, intramedullary nails),etc.

Major surgeries/interventions are expected to require clinical surveillance or hospital treatment >3 days after the surgery/intervention.

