 - $AGG_{phys} = (PF_z \times 0.42402) + (RP_z \times 0.35119) + (BP_z \times 0.31754) + (GH_z \times 0.24954) + (VT_z \times 0.02877) + (SF_z \times (-0.00753)) + (RE_z \times (-0.19206)) + (MH_z \times (-0.22069))$
 - $AGG_{ment} = (PF_z \times (-0.22999)) + (RP_z \times (-0.12329)) + (BP_z \times (-0.09731)) + (GH_z \times (-0.01571)) + (VT_z \times 0.23534) + (SF_z \times 0.26876) + (RE_z \times 0.43407) + (MH_z \times 0.48581)$
- The normalized aggregate scores that will be presented in listings and summaries are determined as:

$$YY_N = 50 + (AGG_{YY} \times 10)$$

where YY is either the physical component score or mental component score.

- Any domain with less than half of the questions answered will have no score calculated. For scales with any questions not answered, but with more than half of

the questions answered, the raw scale should be adjusted in terms of the lowest and highest possible score, including the possible raw range. All other scores will be affected by this change in transformed score. As an example, if question 3a is not answered, then the lowest score for physical functioning is to change from 10 to 9, the highest score is to change from 30 to 27 and the possible raw range from 20 to 18. The new values will be used in determining the transformed score for physical functioning.

Within treatment arm change and between treatment arm change in SF-36 total score as well as the physical and mental component scores between baseline and completion will be tested for any statistical significant differences in a similar manner as described in Section 7.2.1: Haemophilia Joint Health Score (HJHS) Questionnaire.

Items to be included in these tests as part of the secondary efficacy outcomes are:

- Change in physical domain component scores.

Items to be included in these tests as part of the exploratory efficacy outcomes are:

- Change in mental domain component scores.

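### The HJHS total has no rule for joints whose evaluability differs between baseline and completion, so read literally a lost joint scores as improvement

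*SAP*

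**What the plan says.** SAP 7.2.1, Table 1, scores eight items per joint plus a global gait score. Every one of them has the category "Non evaluable: No score", so non-evaluability is foreseen and kept distinct from a score of 0.

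The derivations that follow are sums. A joint total adds up the "Individual item scores per joint within a subject". These are then added over all joints, and gait is put on top. The section sets no minimum number of scored items or joints, does not require the same items at both visits, and does not say when a total is missing.

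On direction it states: "A lower HJHS score indicates a better condition of the joint. Therefore, negative change scores indicate that symptoms have improved".

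Two rank tests compare the two visits. Within each arm the text is: "A Wilcoxon Signed Rank test for paired samples will be used to assess the within treatment arm change in HJHS total score". The arms are compared by a Mann-Whitney U test. Both tests take only changes above half the SD of the baseline totals.

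The other instruments in the same SAP do have a rule. Haemo-SYM (7.2.2) averages the available items and needs at least 50% of them. For SF-36 (7.2.3), "Any domain with less than half of the questions answered will have no score calculated", and otherwise the possible range is rescaled. The EQ-5D utility score (7.2.4) is derived only when all five components are present. SAP 5.5 excludes imputation except where listed, and HJHS is not listed.

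Protocol 11.1.3 has the HJHS scored at the elbows, knees and ankles, at baseline and at the completion/termination visit.

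**The concern.** The total is a sum of penalty points, so its size depends on how many items are scored as well as on joint health. When the set of scored items differs between the two visits, the change score mixes real change with a change in what was measured. A joint that stops being assessable takes its whole baseline score out of the completion total, and the SAP reads the resulting negative change as benefit.

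HJHS is a listed secondary efficacy outcome with within-arm and between-arm tests. It is measured twice only, so no intermediate visit could expose such an artefact. The study is open-label and the joints are scored by the investigator or site staff, so whether a joint is called non-evaluable is an unblinded judgement. What is at stake is the validity of the HJHS change score and its reproducibility between programmers.

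**Working it through.** The plan states no maximum and no power for HJHS, so there is no figure of its own to reproduce. The check applies the SAP's formulas.

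**Scale.** Item maxima from SAP Table 1, in order: swelling 3, duration 1, atrophy 2, crepitus 2, flexion loss 3, extension loss 3, pain 2, strength 4.
- Per joint: 3 + 1 + 2 + 2 + 3 + 3 + 2 + 4 = 20.
- Left and right elbow, knee and ankle (6 joints) plus gait 0 to 4: 6 × 20 + 4 = 124.

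**Artefact on the literal reading.** Let one joint score J at baseline, and let the other joints plus gait total R at both visits.
- Baseline total = J + R. Completion total with that joint unscored = R.
- Change = R − (J + R) = −J. So J = 4 gives −4, J = 10 gives −10 and J = 20 gives −20.
- Non-evaluable at baseline and scored J at completion gives +J.
- Non-evaluable at both visits, or J = 0, gives no artefact.

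**Interaction with the half-SD filter.** The SAP does not say whether the filter is signed or absolute. The baseline SD is not in the documents; assumed values of 10, 15, 20 and 25 give thresholds of 5, 7.5, 10 and 12.5.
- Absolute reading: a false drop enters the tests when J exceeds the threshold. J = 8 enters at SD 10 or 15, J = 12 also at SD 20, and J = 16 also at SD 25.
- Signed reading: every negative change is excluded, real or false, while a false worsening above the threshold is kept.

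**Effect on the rank tests (illustration).** Assumptions: 48 subjects per arm, no true change, change scores with SD 4, no half-SD filter, 2,000 runs, and m subjects in one arm shifted by −10.

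| m | Mean difference between arms | Mann-Whitney rejections | Signed-rank rejections, affected arm |
|---|---|---|---|
| 0 | 0.00 | 4.4% | 4.3% |
| 2 | −0.45 | 5.8% | 6.2% |
| 3 | −0.61 | 6.3% | 8.4% |
| 5 | −1.05 | 11.6% | 17.6% |

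Two or three cases move the tests little; five, all in one arm, move them visibly. The documents do not say how many to expect.

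**Does the remedy work?** Restrict both visits to the same items: R − R = 0 for every J when the rest is unchanged. Rescaling one visit does not achieve this. Take a knee of 10, other joints 14 and gait 1. The baseline total is 25. The completion total rescaled from five joints to six is 14 × 6/5 + 1 = 17.8, so the change is still −7.2. With a knee of 0 the same rescaling gives 17.8 − 15 = +2.8, an error in the other direction.

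**The case against.** The strongest reply is that no sentence in the SAP tells the programmer to treat an unscored item as 0. Table 1 separates the two, and SAP 5.5 bars unlisted imputation. Counting a missing item as the best value is in effect an imputation, so a missing total fits the text at least as well. That stands: the literal sum is one reading. It does not remove the problem. On the other reading, one non-evaluable item removes the subject's total and hence the change, and the SAP still does not choose between the two.

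Other limits also stand. A reader might infer that a joint replaced during the study will be counted as improved. Protocol 22.1.1 lists hip and knee replacement among examples of major surgery, and planned surgery is not a listed withdrawal reason in Protocol 9.3. But neither document says a replaced joint is recorded as non-evaluable, and hips are not scored. Replacement is a possible example only. A reader might also infer that the worst joints are the ones that become non-evaluable, or that one arm would gain. Nothing in the documents establishes either.

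Finally, Protocol 14.4.2 plans only descriptive statistics for HJHS, and subject listings are planned (SAP 7.2), so cases could be noticed. That limits the consequence. But the same change score feeds the descriptive summaries, and a listing does not supply a rule.

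**Conclusion.** The point holds as a gap in the derivation that can give a wrong result. Applied literally, the formulas turn the loss of a joint scored J into an improvement of J points, up to 20 of 124, and the reverse into a worsening. Applied with a missing total, they drop the subject. The plan does not say which.

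The artefact needs evaluability to differ between the two visits and a score above 0 at the visit where the joint was assessed. Its frequency, the direction of any between-arm bias and the net effect of the half-SD filter cannot be determined from the documents. They therefore do not support a claim that HJHS results are biased in favour of either arm. The primary endpoint and the sample size are unaffected. The point merits correction because HJHS is a tested secondary outcome and the remedy is exact and cheap.

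**What to change.** In SAP 7.2.1, define the change in HJHS total as the completion sum minus the baseline sum, each taken only over the joints and items, and gait, that are evaluable at both visits. Report the number of non-evaluable items and joints by arm and visit, so that a reader can see whether the rule was ever used. Do not prorate a single visit's total.

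The cost is a short SAP text and one changed derivation, using item-level data already on the eCRF. The downside is that affected subjects contribute fewer joints, so their change scores cover a smaller part of the scale.

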7.3.4 Patient Reported Outcomes

1. To assess the difference in the SF-36 physical domain and component change scores from baseline to follow-up between subjects in the 10% trough arm and subjects in the 1-3% trough arm
2. To assess the difference in the change of days of physical activity participation from baseline to follow-up between subjects in the 10% trough arm and subjects in the 1-3% trough arm

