14.4.2 Secondary Outcome Measures

- Total, spontaneous, and traumatic ABR, and spontaneous AJBR

For total ABR, spontaneous ABR, traumatic ABR and spontaneous JABR, separate negative binomial models will be used for the second 6 months treatment period (Days 183 to 364) as well as for the complete 12-month treatment period (Days 1 to 364).

The negative binomial model for the bleed rate will include covariates for study arm, stratum, age, and race. The multiple imputations technique will be used for incomplete observation periods as described for the primary endpoints analysis. Subgroups for age and race will be analyzed as well.

For all other outcome measures, descriptive statistics will be presented for the 2 dosing regimens. Point estimates (means and medians) and their 95% CIs will be computed to include:

- Total weight-adjusted consumption of BAX 855 for each prophylactic regimen
- Overall hemostatic efficacy rating at 8 ± 1 h after initiation of treatment and at resolution of bleed
- Number of BAX 855 infusions needed for the treatment of bleeding episodes
- HJHS
- Physical domain and component scores of the SF-36
- Physical Activity Levels

In case of surgeries, descriptive statistics will be performed for the following secondary outcome measures:

- Intra-, post- and perioperative hemostatic efficacy in case of surgery (see Section [22.5.1](#) for details)
- Intra- and postoperative blood loss in case of surgery (see Section [22.5.2](#) for details)

PK parameters before randomization will be summarized descriptively over all subjects to include:

- $AUC_{0-\infty}$, IR at 15-30 minutes post-infusion, $T_{1/2}$, MRT, CL, C_{max} , T_{max} , and V_{ss}

PK parameters after 9 months will be summarized descriptively by prophylactic treatment regimen:

- $AUC_{0-\infty}$, IR at 15-30 minutes post-infusion, $T_{1/2}$, CL, C_{max} , and T_{max}
- IR over time will be displayed as boxplots for the 2 prophylactic regimens

Correlation of VWF:Ag and PK parameters will be assessed by boxplots and Spearman rank correlation coefficient.

Descriptive statistics will be used for the secondary safety outcome measures (see Section [8.4.2.2](#)):

- Occurrence of AEs and SAEs

- Changes in vital signs and clinical laboratory parameters (hematology, clinical chemistry, and lipids)
- Inhibitory antibodies to FVIII, and binding antibodies to FVIII, BAX 855, PEG, and CHO protein

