The methods of analysis for the secondary PROs measures (see Section 8.4.2.3) are described for the following PROs:

- Physical domain and component scores of the SF-36
- Physical activity levels

Change scores from baseline to completion/follow-up will be assessed for each treatment arm and tested using the minimally important difference threshold and the Wilcoxon sign rank test. Differences in the change scores between treatment groups will be tested using the minimally importance difference threshold and the Mann-Whitney U Test.

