7.2.2 Haemophilia Symptom (Haemo-SYM) Questionnaire

The haemophilia symptom questionnaire (Haemo-Sym) is a self reported instrument of measuring symptom severity in patients with haemophilia and has two subscales: pain and bleeds. Lower Haemo-SYM scores indicate fewer symptoms. Therefore, negative change scores indicate that symptoms have improved.

The questions in the Haemo-Sym questionnaire are assigned to the subscales of pain and bleeds as set out in Table 2:

Table 2 Haemo-Sym Questionnaire Subscales

Question (Severity of...)	Subscale
Spontaneous bleeding in my joints (unrelated to injury or activity)	Bleed
Spontaneous bleeding in my muscles (unrelated to injury or activity)	Bleed
Prolonged bleeding after injury in spite of treatment	Bleed

Question (Severity of...)	Subscale
Intense pain because of bleeding event	Bleed
Pain because of swelling in my joints	Pain
Joint pain due to active bleed	Bleed
Bleeding during personal hygiene routine (during shaving, tooth brushing or flossing)	Bleed
Pain because of climbing stairs	Pain
Pain upon waking in the morning	Pain
Constant pain	Pain
Pain because of active arthritis	Pain
Pain in my muscles	Pain
Pain that needs medication	Pain
Joint sensitivity to weather conditions	Pain
Reduced range of joint movement	Pain
Joint deformity	Pain
Sleep disturbance because of pain or bleeds	Pain
Blood in my urine	None
Nose bleeds	None

Results are assigned scores as follows:

- Absent = 0.
- Very mild = 1.
- Mild = 2.
- Moderate = 3.
- Severe = 4.
- Very severe = 5.

The following derivations will be made based of the subject diary reported results:

- The score for each subscale is determined only if at least 50% of the results in that subscale is available. The score should be determined as:

$$Score = \frac{MeanScore}{5} \times 100$$

where MeanScore is the mean of the available results in the particular subscale. If less than 50% of the results in a subscale is available, then no score will be calculated for that subscale.

- The total score for the Haemo-Sym questionnaire should be determined as the mean score of the two subscales should both subscale scores be available.

Within treatment arm change and between treatment arm change in Haemo-SYM total score as well as bleed and pain severity between baseline and completion will be tested for any statistical significant differences in a similar manner as described in Section 7.2.1: Haemophilia Joint Health Score (HJHS) Questionnaire.

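### Between-arm tests of HJHS, SF-36, Haemo-SYM and EQ-5D change ignore baseline and stratum, plan no between-arm difference with a CI, and admit only changes above half an SD

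*SAP*

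**What the plan says.** **Objective.** Protocol 7.3.4 sets out the first patient-reported objective: "To assess the difference in the SF-36 physical domain and component change scores from baseline to follow-up", between the two trough arms.

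**Test.** For HJHS, SAP 7.2.1 says: "A Mann-Whitney U test will be used to assess the between treatment arm change in HJHS total score from baseline to completion". The sample code has treatment as the only class variable. On output the instruction is: "The exact p-value should be selected and presented". For Haemo-SYM (SAP 7.2.2), the within-arm and between-arm changes "will be tested for any statistical significant differences in a similar manner as described in Section 7.2.1". SAP 7.2.3 (SF-36) and 7.2.4 (EQ-5D) refer back in the same way. For SF-36 physical scores, Protocol 14.4.2 agrees: "Differences in the change scores between treatment groups will be tested using the minimally importance difference threshold and the Mann-Whitney U Test". Protocol 14.4.3 does likewise for Haemo-SYM, EQ-5D and the SF-36 mental scores.

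**Who enters the test.** SAP 7.2.1 defines a minimal important difference (MID) as a change above half the SD of the baseline scores. It says that such changes "will be included in both the Wilcoxon Rank sum test as well as the Mann-Whitney U test".

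**Estimates.** For HJHS and SF-36 physical scores by regimen, Protocol 14.4.2 says: "Point estimates (means and medians) and their 95% CIs will be computed to include". SAP 7.2 plans "Summary tables containing descriptive statistics and comparisons, using the Wilcoxon signed rank and Mann-Whitney U tests". Neither document plans a between-arm difference with a CI for these scores.

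**Standing of the outcomes.** Protocol 8.4.2 lists HJHS and SF-36 physical scores as secondary outcome measures. Protocol 8.4.3 lists Haemo-SYM and EQ-5D as exploratory, although Protocol 7.3.1 also names them under the secondary objectives.

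**The concern.** The objective asks for a difference between arms. A rank test gives a p-value, and two separate per-arm intervals are not an interval for the difference. A reader of the results would not learn how large the difference in HJHS or SF-36 physical change is, or how precisely it is known.

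Raw change also carries the measurement noise of the baseline score in full, and a chance baseline imbalance feeds into it through regression to the mean. Conditioning on baseline removes both. The plan already adjusts elsewhere: the bleeding-rate models in Protocol 14.4.2 and SAP 7.1.2 include stratum, age and race. Randomisation has three strata by pre-study regimen and ABR (Protocol 8.5), and the HJHS and questionnaire tests use none of them.

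The half-SD rule raises a separate problem. Whether a subject's change is large enough to enter depends on what happened after randomisation, so the two sets compared are no longer the randomised groups.

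**Working it through.** **The plan's own figure.** The only sample size stated is 48 evaluable per arm for the primary endpoint (40% against 70% bleed-free, two-sided 5%, 80% power). The formula with continuity correction gives 49. Exact enumeration of the corrected chi-square test at 48 per arm gives power 0.8005. The figure reproduces, so 48 per arm is used below. No SD, correlation or power is given for the four scores.

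**Variance.** Let the SD be s at both visits, the baseline-to-completion correlation rho (assumed), and n the number per arm.
- Change score: variance of the effect = 2s²(1 − rho) × 2/n
- ANCOVA on baseline: variance = s²(1 − rho²) × 2/n
- Ratio = (1 − rho²) / [2(1 − rho)] = (1 + rho)/2

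**Smallest difference detectable** with 80% power, in units of s: (1.960 + 0.842) × √(2/48) = 0.572, multiplied by √[2(1 − rho)] for change and √(1 − rho²) for ANCOVA.

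| rho | variance ratio | reduction | change score | ANCOVA |
|---|---|---|---|---|
| 0.5 | 0.75 | 25% | 0.57 | 0.50 |
| 0.7 | 0.85 | 15% | 0.44 | 0.41 |
| 0.9 | 0.95 | 5% | 0.26 | 0.25 |

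**Simulated power.** Normal data, 48 per arm, 3,000 runs, one arm shifted upward by an assumed 0.5 SD. The last two columns apply the half-SD rule before the Mann-Whitney test, first as written (change above +½ SD), then read as absolute change.

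| rho | Mann-Whitney, all changes | ANCOVA | filter as written | filter on absolute change |
|---|---|---|---|---|
| 0.5 | 66% | 79% | 11% | 62% |
| 0.7 | 87% | 92% | 15% | 79% |
| 0.9 | about 100% | about 100% | 17% | 89% |

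With no true difference, Mann-Whitney on all changes rejects in 5.5%, 4.8% and 4.8% of runs, so it holds its level.

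**What the filter does.** With no true change, the rule as written keeps 31%, 26% and 13% of subjects. All kept changes are positive, so the within-arm signed-rank test, which uses the same rule, rejects in 99.9%, 99.3% and 60% of runs. SAP 7.2.1 treats negative HJHS change as improvement, so the literal rule would keep only subjects whose joints worsened.

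The gain from adding the stratum cannot be computed from the documents.

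**The case against.** The strongest reply is that nothing here is invalid. In a 1:1 randomised trial an unadjusted Mann-Whitney test on all changes is sound, and the simulation confirms it. A reader might infer that the comparison is biased. Chance imbalance matters only conditionally on the baseline observed; over randomisation there is no bias. That part of the reply stands for the unfiltered test.

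A reader might also infer that the plan yields nothing but a p-value and leaves the objective wholly unanswered, or that the baseline is wasted. The documents do not support either reading. Protocol 14.4.2 plans per-regimen means and medians with 95% CIs for HJHS and SF-36 physical scores, and SAP 7.2 adds descriptive tables for all four instruments. Baseline is used, by subtraction. What is missing is narrower: the between-arm difference, its CI, and adjustment.

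The gain may be small. HJHS scores atrophy, crepitus and loss of motion, which may change little in 12 months; if rho is near 0.9 the saving is 5%. This is fair, and it is why the range is shown. The absolute power figures also do not transfer directly to SF-36 (age 14 and over) or Haemo-SYM (age 18 and over), where numbers may be below 48 per arm.

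Finally, a rank-based ANCOVA gives no mean difference by itself, and leaving open which scores count as skewed invites a data-driven choice in an open-label trial. Both points are right, and the fix allows for them.

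**Conclusion.** The point holds as one of efficiency and reporting. For two secondary outcome measures and two exploratory ones, the plan tests change without adjusting for baseline or stratum and provides no between-arm difference with a CI. Under equal SDs and an assumed rho of 0.5 to 0.9, baseline adjustment lowers the variance by 25% down to 5%. The power figures rest further on normal data, 48 per arm and an assumed 0.5 SD effect.

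It would go too far to say that the planned rank test is wrong in itself: on all subjects' changes it is valid. The half-SD rule in SAP 7.2.1 is the more serious matter. Under the same assumptions it cuts simulated power to 11–17% as written, or 62–89% if absolute change is meant. Because it selects on a post-randomisation outcome, adding covariates would not cure it.

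**What to change.** In SAP 7.2.1 to 7.2.4:

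- Analyse the completion score in all FAS subjects with data by ANCOVA with arm, baseline score and randomisation stratum. Report the adjusted between-arm difference with its 95% CI.
- Prespecify which scores, if any, use a rank-based version stratified or adjusted for the same factors. Give a Hodges-Lehmann difference with 95% CI for those.
- Remove the half-SD filter from the within-arm and between-arm tests. Use the MID only for interpretation or a responder summary.
- Keep the Mann-Whitney test on all subjects' changes as supportive.
- Record the change in SAP 5.8, since Protocol 14.4.2 and 14.4.3 name the Mann-Whitney test and the MID threshold for the patient-reported scores.

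The cost is a documented departure from the protocol's stated test and a little more analysis work. No new data are needed.
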